If a client is willing and able to complete additional surveys, a time will be scheduled where a HEARS Staff member will ask and collect their answers virtually.

Virtual surveys will be conducted in the order listed in Section 3 (same as in-person visits) other than if a client indicates they are not interested in completing the entire set of surveys.

Surveys will be prioritized in this order and as many as they are willing to complete will be completed (including offering to split up the meetings):

- 1. HHIE
- 2. UCLA
- 3. PHQ9
- 4. IOI-AI
- 5. Device Use
- 6. Program Evaluation
- 7. SF-12
- 8. SNI
- 9. VOL
- 10. Tech-SE
- 11. HEARS Basic Assessment
- 12. LSEQ
- b. Study duration and number of study visits required of research participants.

The study will take place over approximately 18 months. Details are summarized in Figure 4.

[figure not shown]

Figure 4: Overall Study Design and Timeline

An information session with a follow-up hearing screening will require an estimated total of 90 minutes. The meeting will introduce the study and HEARS program to interested participants, and screen consenting participants for study eligibility. Information sessions will be delivered by trained CHW's and the study staff.

Following attendance at an information session, study staff will meet with interested residents to obtain oral screening consent to undergo hearing screening and to gather other screening measures related to eligibility criteria. The participant will be advised about his/her eligibility. If eligible participants are interested in proceeding, the study staff will review the study, the associated written consent form, and obtain written consent. Participants will then complete baseline measurements and be randomized into either the immediate or delayed treatment groups. The baseline questionnaires will take approximately 45-50 minutes to complete.

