During the first meeting, the CHW will introduce the HEARS program and review communication strategies and basics of age-related hearing loss, as well as options for amplification including the differences between over-the-counter amplifiers used in the program versus conventional hearing aids typically acquired through audiologists. The second meeting will consist of a step-by-step fitting and orientation to the participant’s amplifier of choice. Based on the needs of the participant and the discretion of the CHW, additional meetings may occur to ensure the participant is comfortable using his/her amplifier independently.

Study Design: The study design is an open label, two-arm, parallel group trial: participants are randomized 1:1 to a group which receives the HEARS intervention immediately (the ‘immediate group’, or ‘Wave 1’) or receives the HEARS intervention after the 3-month primary endpoint (the ‘delayed group’, or ‘Wave 2’). Randomization is stratified by study site to maximize within-building balance in treatment allocation.

Intervention Description: The intervention (“treatment”) consists of aural rehabilitation, which includes basic education on age-related hearing loss and communication strategies, and provision of an over-the-counter amplifier. The amplifier devices utilized in this study are low-cost, self-fit amplifiers that are currently available over the counter, directly to consumers: the Sound World Solutions (SWS) Sidekick and Sonic Technology’s SuperEar SE9000. Neither of these devices are medical devices regulated by the FDA. The session will include fitting the device and a step-by-step orientation to the device. The intervention will be delivered by a trained community health worker (CHW) in the participant’s community. Treatment would be considered a failure if individuals do not complete the two-session intervention (i.e., did not attend all scheduled intervention meetings).

Sample Size Justification: The primary outcome will be the Hearing Handicap for the Elderly Screening Version (HHIE-S) measured at 3-months post-intervention. The HHIE-S is a validated 10-item questionnaire (range: 0-40 points) to assess perceived effects of hearing loss among older adults (Weinstein et al., 1986). The Baltimore HEARS pilot study showed excellent test-retest reliability of the HHIE in the target population and demonstrated a 'large' effect size on this outcome (Cohen's $D=0.74$, $N=15$).

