We hypothesize that assignment to the immediate treatment group will have higher average HHIE scores at follow-up compared to those assigned to the delayed treatment group, who will not receive the intervention prior to the 3-month primary endpoint: a superiority hypothesis.

Effect Size	N per Arm	Total Sample Size	10% Attrition	20% Attrition
0.60	60	120	134	150
0.65	51	102	114	128
0.70	44	88	98	110
0.75	39	78	88	98
0.80	34	68	76	86
0.85	31	62	70	78
0.90	27	54	60	68

Table 1: Sample sizes necessary to achieve 90% power while maintaining a type I error rate at 0.05 using a two-sample t-test. These sample sizes are adjusted to account for potential loss to follow up.

A target sample size of 150 participants would ensure adequate power to test a clinically meaningful effect on the primary outcome, even with 20% attrition.

Framework: All hypotheses are being tested within a superiority framework. Individuals will be randomized to receive the intervention immediately (i.e. prior to the 3-month post-randomization visit, where the primary outcome is obtained), or to a wait-list control (i.e. receive the intervention after the primary outcome is obtained). For the primary outcome, it is hypothesized that individuals randomized to receive the intervention immediately will have greater declines in hearing handicap from baseline, as measured by the HHIE-S, than those assigned to the wait list control. Similarly, immediate treatment is hypothesized to be superior to wait list controls on all secondary outcomes.

Interim Analyses and Stopping Guidance: Given the short follow up window and minimal risk to participants, no interim analyses for efficacy or futility will be conducted. There is no anticipated need to stop the trial for safety concerns.

Timing of the Final Analysis: Data for the primary outcome will be considered complete after the last participant's last visit window for the primary outcome has closed. These records will be locked, although post-intervention follow-up data will continue to be collected. Efficacy of the intervention will be assessed only using information obtained at baseline and at the primary endpoint (3 months post-randomization). All data will be complete after the last participant's last window for the 12-month post-intervention visit has closed.

Timing of Outcome Assessments: A table of study visits and their corresponding visit windows is given in Table 2.

Study Visit	Immediate Treatment: Wave 1	Delayed Treatment: Wave 2

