- Missing Primary outcome: number of participants who did not complete primary outcome

Withdrawals, missed visits, and loss to follow up will be reported in consort diagram by study visit (3, 6, and 12-months post-enrollment). In the primary analysis, only 3-month post-randomization information will be reported, with other attrition reported in subsequent publications.

Scoring of Outcomes: Instruments with any missing items (e.g. “Refused”, “Don’t Know”) will be coded as missing unless there are published criteria for handling missing items. For the Cohen Social Network Index, social network size (SNS) will be scored using published criteria that involve top-coding groups of size greater than 6 at 7 individuals in item 12 – this keeps the scoring of item 12 consistent with items 5-11 and limits the range of SNS between 0-103.

Baseline patient characteristics: Baseline characteristics will be summarized in aggregate and by treatment arm as specified in Table 3 below.

Measure	Domain	Type	Summary
Age	Demographics	Continuous	Mean (SD)
Sex	Demographics	Categorical	Frequency (%)
Race/ethnicity	Demographics	Categorical	Frequency (%)
Living arrangement	Demographics	Categorical	Frequency (%)
Education	Demographics	Categorical	Frequency (%)
Monthly household income	Demographics	Categorical	Frequency (%)
MoCA	Cognition	Continuous	Mean (SD)
Speech-Frequency Pure Tone Average	Hearing	Continuous	Mean (SD)
Hearing loss category	Hearing	Categorical	Frequency (%)
Prior hearing screening	Hearing	Categorical	Frequency (%)
Prior hearing aid use	Hearing	Categorical	Frequency (%)
HHIE-S	Hearing & Communication	Continuous	Mean (SD)
UCLA Loneliness Scale	Social Isolation & Loneliness	Continuous	Mean (SD)
PHQ-9	Depression	Continuous	Mean (SD)
Cohen SNI: Network Diversity	Social Network	Continuous	Mean (SD)
Cohen SNI: Social Network Size	Social Network	Continuous	Median (IQR)
SF-12 Mental Component Score	Health Related Quality of Life	Continuous	Mean (SD)
SF-12 Physical Component Score	Health Related Quality of Life	Continuous	Mean (SD)
REALM-SF	Health Literacy	Continuous	Mean (SD)
AATCQ Computer Self Efficacy	Technology Self Efficacy	Continuous	Mean (SD)
AATCQ Listening Device Interest	Technology Self Efficacy	Continuous	Mean (SD)
AATCQ Listening Device Self Efficacy	Technology Self Efficacy	Continuous	Mean (SD)
ALSEQ Listening Self Efficacy	Listening Self Efficacy	Continuous	Mean (SD)
Own smartphone	Technology Self Efficacy	Categorical	Frequency (%)

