Used a computer within past month	Technology Self Efficacy	Categorical	Frequency (%)
Used text or email within past month	Technology Self Efficacy	Categorical	Frequency (%)

Table 3: Baseline characteristics of participants to be summarized. Tests of statistical significance will not be undertaken for baseline characteristics; rather the clinical importance of any imbalance will be noted. Hearing loss in the better hearing ear will be categorized using the speech frequency pure tone

average (PTA in db HL) as Normal (≤ 25) Mild ($25 < \text{PTA} \leq 40$), Moderate or greater (>40). Abbreviations – MoCA: Montreal Cognitive Assessment; SNI: Social Network Index; SF-12: Short Form 12; AATCQ: Adapted Attitudes Towards Computers Questionnaire; REALM-SF: Rapid Estimate of Adult Literacy in Medicine – Short Form; ALSEQ: Adapted Listening Self-Efficacy Questionnaire

Section 6: Analysis

Study Outcomes: All study outcomes are listed in Table 4 below.

Outcome Measure	Outcome Type	Transformation	Units [Range]
HHIE-S	Primary	Change from Baseline	Points [-40, 40]
UCLA Loneliness Scale	Secondary	Change from Baseline	Points [-60, 60]
PHQ-9	Secondary	Change from Baseline	Points [-27, 27]
SF-12 Mental Component Score (MCS)	Secondary	Change from Baseline	Points [-41.7, 41.7]
SF-12 Physical Component Score (PCS)	Secondary	Change from Baseline	Points [-32.6, 32.6]
SNI: Network Diversity	Secondary	Change from Baseline	Points [-12, 12]
SNI: Social Network Size	Secondary	Change from Baseline	Points [-103, 103]
Valuation of Life (VoL)	Secondary	Change from Baseline	Points [-52, 52]
ALSEQ Total Score	Secondary	Change from Baseline	Points [-50, 50]
AATCQ Computer Self Efficacy	Secondary	Change from Baseline	Points [-20, 20]
AATCQ Device Self Efficacy	Secondary	Change from Baseline	Points [-20, 20]
AATCQ Device Interest	Secondary	Change from Baseline	Points [-20, 20]
ALSEQ Subscale: Dialogue in Quiet (DQ)	Exploratory	Change from Baseline	Points [-10, 10]
ALSEQ Subscale: Directed Listening (DL)	Exploratory	Change from Baseline	Points [-20, 20]
ALSEQ Subscale: Complex Listening (CL)	Exploratory	Change from Baseline	Points [-20, 20]
Hearing Related Knowledge	Exploratory	Untransformed Score	Points [0, 8]

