Missing Data: As stated above, instruments with any missing items (e.g. “Refused”, “Don’t Know”) will be coded as missing unless there are published criteria for handling missing items. Frequency and patterns of missing data will be tabulated in aggregate and by treatment arm. The doubly robust estimator is valid under the assumption that data are missing at random: that the degree of missingness does not depend on unobserved variables or the values of the missing data. Additionally, a

supplementary table will compare baseline characteristics between those with missing 3-month post-randomization outcomes to those with complete data both in aggregate and by treatment arm.

If an individual's baseline outcome is missing, and the outcome of interest is a baseline change score, imputed values will only be used to calculate propensity scores and inverse probability weights: since the original value was not observed, the change from baseline will be considered missing.

Risks and Potential Harm: The risks involved in participation in the study are believed to be low. There is a theoretical risk of noise exposure related to use of an amplification device, primarily if the device malfunctions. The risk of noise exposure is minimized with volume limitations as part of the device design. All products used in the study are commercially available and all models used in the study are considered over-the-counter devices.

Other than the intervention failing to produce an effect, there are no known possible adverse effects documented in the literature or experienced in prior pilot studies involving over-the-counter amplification devices and the HEARS intervention. All devices and intervention materials have been either previously used in pilot studies or are currently used by consumers in the United States with no known harmful effects.

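### The SAP's missing-item rule counts a *Don't Know* answer as missing data, with no exception for the exploratory hearing-knowledge score, where that answer is probably a valid low score

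*SAP*

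**What the plan says.** The rule appears twice in the SAP: in Section 5 under Scoring of Outcomes and in Section 6 under Missing Data. The second statement reads: "instruments with any missing items (e.g. “Refused”, “Don’t Know”) will be coded as missing unless there are published criteria for handling missing items". The only exemption is for instruments with published criteria.

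Section 5 follows the rule at once with special scoring for one instrument: "will be coded as missing unless there are published criteria for handling missing items. For the Cohen Social Network Index". Nothing comparable is given for "Hearing Related Knowledge", which Table 4 lists as exploratory, untransformed, with a range of 0 to 8 points. The Protocol's COVID-19 survey order includes a "HEARS Basic Assessment". This may be the source of the score, but neither document says so.

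In the first intervention meeting (SAP Section 3) the CHW is to "review communication strategies and basics of age-related hearing loss". The waitlist arm is to "receive the intervention after the primary outcome is obtained", so it is untaught at the 3-month comparison.

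On validity, Section 6 says: "The doubly robust estimator is valid under the assumption that data are missing at random". It spells this out as missingness that does not depend on unobserved variables or on the missing values. The weight and outcome models use the baseline value of the outcome, age, PTA and treatment arm.

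**The concern.** On an attitude or symptom scale, *Don't Know* is non-response. On a test with right and wrong answers it is a response, and it signals a low score. A rule that blanks the test after one such answer never removes a participant who knows everything, and it removes others more often the less they know. For this outcome the scoring rule therefore works against the assumption on which the estimator relies.

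The covariates are unlikely to repair this. Age and PTA are at best weak proxies for hearing knowledge. Table 4's caption says every outcome is assessed at baseline, but Table 3 does not list knowledge. If a baseline score exists, the same rule would blank it for the same people, and Section 6 mean-imputes missing baseline values. Tabulating missingness by arm would show the loss without correcting it.

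At stake is the one Table 4 outcome named as hearing knowledge, and so the reading of whether the education component taught anything. It is exploratory, so no confirmatory claim depends on it.

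**Working it through.** **Figures in the plan.** The documents give no expected knowledge effect and no *Don't Know* rate. The only design figures are in SAP Table 1, for the HHIE-S. They reproduce in every row with a noncentral-t calculation (effect size 0.60, 60 per arm, power 90.3%; 150 in total after 20% attrition). This point does not affect them.

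**Assumptions, none of them in the documents.** Eight items, each marked right or wrong. A participant knows an item with probability *k*. An unknown item is answered *Don't Know* with probability *q* (the readiness to say so); otherwise it is guessed, correctly with probability *g*. The exploratory outcome is taken to be analysed with the same estimator as the others.

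**Loss of scores.** If *Don't Know* is given independently with probability *p* on each item, the rule discards 1 − (1 − p)^8 of tests: 1 − 0.95^8 = 34% at p = 5%, and 1 − 0.90^8 = 57% at p = 10%.

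**Closed form for the effect.** Per item, the chance of a correct answer is a = k + (1 − k)(1 − q)g, and the chance of an answer other than *Don't Know* is b = k + (1 − k)(1 − q).

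- *Don't Know* marked incorrect: effect = 8(a₁ − a₀).
- SAP rule: effect = 8(a₁/b₁ − a₀/b₀), with a fraction b^8 of scores kept in each arm.

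Take k = 0.5 in the waitlist arm and 0.7 in the taught arm, g = 0.5 and q = 0.2 in both. Then a₀ = 0.70, b₀ = 0.90, a₁ = 0.82, b₁ = 0.94. Marked incorrect: 8 × 0.12 = 0.96. SAP rule: 8 × (0.8723 − 0.7778) = 0.757, which is 21% smaller. Scores kept: 0.90^8 = 43% and 0.94^8 = 61%.

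| q waitlist / taught | Kept waitlist / taught | Marked incorrect | SAP rule | Change |
|---|---|---|---|---|
| 0 / 0 | 100% / 100% | 0.80 | 0.80 | none |
| 5% / 5% | 82% / 89% | 0.84 | 0.791 | 6% smaller |
| 50% / 50% | 10% / 27% | 1.20 | 0.627 | 48% smaller |
| 30% / 10% | 27% / 78% | 1.28 | 0.534 | 58% smaller |
| 10% / 30% | 66% / 47% | 0.64 | 0.972 | 52% larger |

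**Simulation with the SAP's estimator.** 150 participants, 1:1, 1,000 replicates, knowledge varying between people, g = 0.5. Propensity and missingness weights capped at 20, then quasibinomial g-computation with age and PTA, and no baseline knowledge score.

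| q waitlist / taught | Kept waitlist / taught | Marked incorrect | SAP rule | Change |
|---|---|---|---|---|
| 5% / 5% | 82% / 88% | 0.78 | 0.72 | 8% smaller |
| 10% / 10% | 67% / 78% | 0.80 | 0.69 | 14% smaller |
| 20% / 20% | 46% / 62% | 0.88 | 0.63 | 28% smaller |
| 40% / 40% | 22% / 40% | 1.04 | 0.47 | 55% smaller |
| 20% / 10% | 46% / 78% | 1.01 | 0.47 | 53% smaller |
| 10% / 30% | 67% / 49% | 0.55 | 1.00 | 81% larger |

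At q = 20% in both arms, waitlist participants who are kept score about 1.5 points more than those removed. With no true effect and equal q, both scorings give about 0.

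**A second simulation** used g = 0.25, average knowledge of 50% and about 70%, a mean-imputed baseline score in the models, and weighted linear regression without age or PTA. For q of 5, 10, 20 and 40% in both arms, the SAP rule gave 1.28, 1.25, 1.16 and 0.85 points against 1.33, 1.36, 1.42 and 1.48 marked incorrect: 4, 8, 18 and 43% smaller. Including a baseline score did not remove the bias.

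**The reference also moves.** Marking *Don't Know* as incorrect is affected by readiness to guess. With equal knowledge in both arms (k = 0.6, g = 0.5) and q = 10% waitlist, 30% taught, it gives 8 × (0.74 − 0.78) = −0.32, while the SAP rule gives 8 × (0.74/0.88 − 0.78/0.96) = +0.23. Rescoring keeps everyone in the analysis but does not remove this dependence, so the counts by arm are needed as well.

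**The case against.** The strongest reply is that the premise is inferred. The documents show no items, answer format or scoring key. The *Don't Know* in the rule is a generic example for all instruments, not evidence that this test offers it. Published criteria may exist, or the score may already treat *Don't Know* as incorrect. All of that stands, and it makes the finding conditional. It does not remove it: the rule is stated for all instruments, an exception is written out for the Social Network Index, and none is written for the knowledge score. An analyst following the text would blank the test.

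Three stronger readings are tempting and are not supported.

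- *The rule certainly shrinks the effect and mostly removes controls.* This needs equal readiness to say *Don't Know* in the two arms, or greater readiness in the waitlist arm. If taught participants are sufficiently readier to admit not knowing, the effect is overstated. The documents give no response rates.
- *The rule also removes the most impaired people through MoCA and REALM-SF.* Neither is a Table 4 outcome. REALM-SF is a baseline descriptor; MoCA is a baseline descriptor and defines one exploratory subgroup. Both are named instruments to which the published-criteria exception may apply, and nothing shows that their responses are coded *Don't Know*.
- *The trial's main result is at risk.* It is not. The score is labelled exploratory.

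It is also fair that the planned tables of missingness by arm, and of baseline characteristics by missingness, would expose differential loss. They would not correct the estimate.

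**Conclusion.** The point holds in conditional form. The SAP states a rule that, applied as written to a right/wrong test on which *Don't Know* can be recorded, deletes valid low scores and makes missingness depend on the outcome, against its own missing-at-random condition.

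With a real effect and equal readiness in the two arms, attenuation was about 4% to 55% across the two simulations, for *Don't Know* on 5% to 40% of unknown items. Every rate is assumed, and the percentages are relative to marking *Don't Know* incorrect. The sign depends on behaviour that the documents do not describe. If *Don't Know* is never recorded on this test, nothing changes.

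The consequence is confined to one exploratory outcome. The primary HHIE-S analysis, the listed secondary outcomes and the sample size are unaffected.

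**What to change.** In SAP Section 5 (Scoring of Outcomes) and Section 6 (Missing Data), add after the missing-item rule:

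> For Hearing Related Knowledge, *Don't Know* scores 0 (incorrect) for that item; refused or unasked items remain missing.

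State the number of items and the scoring key in the same place. Report *Don't Know* counts by arm, and show the result under the current rule as a sensitivity analysis.

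The cost is a sentence or two, a recode and one extra run of the model, provided that item-level responses were kept. SAP Section 1 says that all changes after version 1.0 followed unblinding of outcomes, so this change must be labelled the same way. Showing both scorings lets readers see that it was not chosen for its result. If the test has no *Don't Know* option, a sentence saying so closes the point.
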